## 7.2.1 Definition of an Overdose for This Protocol and Reporting of Overdose to the Sponsor and to Merck

For purposes of this trial, an overdose of pembrolizumab will be defined as any dose of 1,000 mg or greater (≥5 times the indicated dose). No specific information is available on the treatment of overdose of pembrolizumab. Appropriate supportive treatment should be provided if clinically indicated. In the event of overdose, the subject should be observed closely for signs of toxicity. Appropriate supportive treatment should be provided if clinically indicated.

If an adverse event(s) is associated with ("results from") the overdose of a Merck product, the adverse event(s) is reported as a serious adverse event, even if no other seriousness criteria are met.

If a dose of Merck's product meeting the protocol definition of overdose is taken without any associated clinical symptoms or abnormal laboratory results, the overdose is reported as a non-serious Event of Clinical Interest (ECI), using the terminology "accidental or intentional overdose without adverse effect."

All reports of overdose with and without an adverse event must be reported within 24 hours to the Sponsor and within 2 working days hours to Merck Global Safety. (Attn: Worldwide Product Safety; [contact])

## 7.2.2 Reporting of Pregnancy and Lactation to the Sponsor and to Merck

Although pregnancy and lactation are not considered adverse events, it is the responsibility of investigators or their designees to report any pregnancy or lactation in a subject (spontaneously reported to them), including the pregnancy of a male subject's female partner that occurs during the trial or within 120 days of completing the trial completing the trial, or 30 days following cessation of treatment if the subject initiates new anticancer therapy, whichever is earlier. All subjects and female partners of male subjects who become pregnant must be followed to the completion/termination of the pregnancy. Pregnancy outcomes of spontaneous abortion, missed abortion, benign hydatidiform mole,

blighted ovum, fetal death, intrauterine death, miscarriage and stillbirth must be reported as serious events (Important Medical Events). If the pregnancy continues to term, the outcome (health of infant) must also be reported.

Such events must be reported within 24 hours to the Sponsor and within 2 working days to Merck Global Safety. (Attn: Worldwide Product Safety; [contact])

## 7.2.3 Immediate Reporting of Adverse Events to the Sponsor and to Merck

## 7.2.3.1 Serious adverse events

A serious adverse event is any adverse event occurring at any dose or during any use of Merck's product that:

- Results in death;
- Is life threatening;
- Results in persistent or significant disability/incapacity:
- Results in or prolongs an existing inpatient hospitalization;
- Is a congenital anomaly/birth defect;
- Is a new cancer (that is not a condition of the study);
- Is associated with an overdose:
- Is an important medical event

Refer to Table 6 for additional details regarding each of the above criteria.

Any serious adverse event, or follow up to a serious adverse event, including death due to any cause other than progression of the cancer under study that occurs to any subject from the time the consent is signed through 30 days following cessation of treatment, or the initiation of new anti-cancer therapy, whichever is earlier, whether or not related to Merck product, must be reported **within 24 hours** to the Sponsor and **within 2 working days** to Merck Global Safety.

Non-serious Events of Clinical Interest will be forwarded to Merck Global Safety and will be handled in the same manner as SAEs.

Additionally, any serious adverse event, considered by an investigator who is a qualified physician to be related to Merck product that is brought to the attention of the investigator at any time outside of the time period specified in the previous paragraph also must be reported immediately to the Sponsor and to Merck.

## SAE reports and any other relevant safety information are to be forwarded to the Merck Global Safety [contact]

A copy of all 15 Day Reports and Annual Progress Reports is submitted as required by FDA, European Union (EU), Pharmaceutical and Medical Devices agency (PMDA) or other local regulators. Investigators will cross reference this submission according to local regulations to the Merck Investigational Compound Number (IND, CSA, etc.) at the time of submission.

Additionally investigators will submit a copy of these reports to Merck & Co., Inc. (Attn: Worldwide Product Safety; [contact]) at the time of submission to FDA.

All subjects with serious adverse events must be followed up for outcome.

#### 7.2.3.2 Events of clinical interest

Selected non-serious and serious adverse events are also known as Events of Clinical Interest (ECI) and must be recorded as such on the Adverse Event case report forms/worksheets and reported **within 24 hours** to the Sponsor and **within 2 working days** to Merck Global Safety (Attn: Worldwide Product Safety; [contact]). Events of clinical interest for this trial include:

- 1. An overdose of Merck product, as defined in Section 7.2.1 Definition of an Overdose for This Protocol and Reporting of Overdose to the Sponsor, that is not associated with clinical symptoms or abnormal laboratory results.
- 2. An elevated AST or ALT lab value that is greater than or equal to 3X the upper limit of normal and an elevated total bilirubin lab value that is greater than or equal to 2X the upper limit of normal and, at the same time, an alkaline phosphatase lab value that is less than 2X the upper limit of normal, as determined by way of protocol-specified laboratory testing or unscheduled laboratory testing.\*

\*Note: These criteria are based upon available regulatory guidance documents. The purpose of the criteria is to specify a threshold of abnormal hepatic tests that may require an additional evaluation for an underlying etiology. The trial site guidance for assessment and follow up of these criteria can be found in the Investigator Trial File Binder (or equivalent).

#### 3. Additional adverse events:

A separate guidance document has been provided entitled "Event of Clinical Interest Guidance Document" (previously entitled, "Event of Clinical Interest and Immune-Related Adverse Event Guidance Document"). This document can be found in Appendix 4 and provides guidance regarding identification, evaluation and management of ECIs and irAEs.

ECIs (both non-serious and serious adverse events) identified in this guidance document from the date of first dose through 30 days following cessation of treatment, need to be reported **within 24 hours** to the Sponsor and **within 2 working days** to Merck Global Safety. (Attn: Worldwide Product Safety; [contact]), regardless of attribution to study treatment, consistent with standard SAE reporting guidelines.

Subjects should be assessed for possible ECIs prior to each dose. Lab results should be evaluated and subjects should be asked for signs and symptoms suggestive of an immune-related event. Subjects who develop an ECI thought to be immune-related should have additional testing to rule out other etiologic causes. If lab results or symptoms indicate a possible immune-related ECI, then additional testing should be performed to rule out other etiologic causes. If no other cause is found, then it is assumed to be immune-related.

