#### 5.2.1.2 Dose Modification

Adverse events (both non-serious and serious) associated with pembrolizumab exposure may represent an immunologic etiology. These adverse events may occur shortly after the first dose or several months after the last dose of treatment. Pembrolizumab must be withheld for drug-related toxicities and severe or life-threatening AEs as per **Table 7** below. See Section 5.6.1 and Events of Clinical Interest Guidance Document for supportive care guidelines, including use of corticosteroids.

Table 7. Dose Modification Guidelines for Drug-Related Adverse Events

Toxicity	Hold Treatment For Grade	Timing for Restarting Treatment	Discontinue Subject
Diarrhea/Colitis	2-3	Toxicity resolves to Grade 0-1.	Toxicity does not resolve within 12 weeks of last dose or inability to reduce corticosteroid to 10 mg or less of prednisone or equivalent per day within 12 weeks.
	4	Permanently discontinue	Permanently discontinue
AST, ALT, or Increased Bilirubin	2	Toxicity resolves to Grade 0-1	Toxicity does not resolve within 12 weeks of last dose.
	3-4	Permanently discontinue (see exception below) 	Permanently discontinue
Type 1 diabetes mellitus (if new onset) or Hyperglycemia	T1DM or 3-4	Hold pembrolizumab for new onset Type 1 diabetes mellitus or Grade 3- 4 hyperglycemia associated with evidence of beta cell failure.	Resume pembrolizumab when patients are clinically and metabolically stable.
Hypophysitis	2-3	Toxicity resolves to Grade 0-1	Toxicity does not resolve within 12 weeks of last dose or inability to reduce corticosteroid to 10 mg or less of prednisone or equivalent per day within 12 weeks.
	4	Permanently discontinue	Permanently discontinue
Hyperthyroidis m	3	Toxicity resolves to Grade 0-1	Toxicity does not resolve within 12 weeks of last dose or inability to reduce corticosteroid to 10 mg or less of prednisone or equivalent per day within 12 weeks.
	4	Permanently discontinue	Permanently discontinue
Hypothyroidism	2-4	Therapy with pembrolizumab can be continued while treatment for the thyroid disorder is instituted	Therapy with pembrolizumab can be continued while treatment for the thyroid disorder is instituted.
Infusion Reaction	3-4	Permanently discontinue	Permanently discontinue
Pneumonitis	2	Toxicity resolves to Grade 0-1	Toxicity does not resolve within 12 weeks of last dose or inability to reduce corticosteroid to 10 mg or less of prednisone or equivalent per day within 12 weeks.

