## 5.5.1 Acceptable Concomitant Medications

All treatments that the investigator considers necessary for a subject's welfare may be administered at the discretion of the investigator in keeping with the community standards of medical care. All concomitant medication will be recorded in the source documentation including all prescription, over-the-counter (OTC), herbal supplements, and IV medications and fluids. If changes occur during the trial period, documentation of drug dosage, frequency, route, and date may also be included on the source documentation. Only those concomitant medications which are considered immunosuppressive such as steroids will be recorded in the CRF.

All concomitant medications received within 28 days before the first dose of trial treatment and 30 days after the last dose of trial treatment should be recorded. Concomitant medications administered after 30 days after the last dose of trial treatment should be recorded for SAEs as defined in Section 7.2 and ECIs as per the ECI guidance document.

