The End of Treatment and Follow-up visit procedures are listed in Section 6 (Protocol Flow Chart) and Section 7.1.5 (Visit Requirements). After the last dose of study drug, each subject will be followed for 30 days for adverse event monitoring (serious adverse events will be collected for 90 days after the end of treatment as described in Section 7.2.3.1). Subjects who discontinue for reasons other than progressive disease will have post-treatment follow-up for disease status until disease progression, initiating a non-study cancer treatment, withdrawing consent or becoming lost to follow-up. After documented disease progression each subject will be followed by telephone for overall survival until death, withdrawal of consent, or the end of the study, whichever occurs first.

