### 7.1.7.1 Safety follow-up visit

The mandatory Safety Follow-Up Visit should be conducted approximately 30 days after the last dose of trial drug administration or before the initiation of a new anti-cancer treatment, whichever comes first. All AEs that occur prior to the Safety Follow-Up Visit should be recorded. Subjects with an AE of Grade > 1 will be followed until the resolution of the AE to Grade 0-1 or until the beginning of a new anti-neoplastic therapy, whichever occurs first. SAEs that occur within 90 days of the end of treatment or before initiation of a new anti-cancer treatment should also be followed and recorded. Subjects who are eligible for retreatment with pembrolizumab (as described in Section 7.1.7.3) may have up to two safety follow-up visits, one after the Treatment Period and one after the Second Course Phase.

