#### 7.1.7.2 Follow-up visits

Subjects who discontinue trial treatment for a reason other than disease progression will move into the Follow-Up Phase and should be assessed every 8 weeks (56  $\pm$  7 days) by radiologic imaging to monitor disease status. After 1 year, the imaging time point will occur

every 12 weeks (± 7 days). Every effort should be made to collect information regarding disease status until the start of new anti-neoplastic therapy, disease progression, death, end of the study or if the subject begins retreatment with pembrolizumab as detailed in Section 7.1.7.3. Information regarding post-study anti-neoplastic treatment will be collected if new treatment is initiated.

Subjects who are eligible to receive retreatment with pembrolizumab according to the criteria in Section 7.1.7.3 will move from the follow-up phase to the Second Course Phase when they experience disease progression.

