All adverse events will be recorded from C1D1 through 30 days following cessation of treatment and at each examination on the Adverse Event case report forms/worksheets. The reporting timeframe for adverse events meeting any serious criteria is described in section 7.2.3.1.

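### New non-serious immune-related events starting more than 30 days after the last dose have no scheduled collection, and the windows for serious events conflict

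*Combined protocol and SAP*

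**What the plan says.** On timing, Section 5.2.1.2 (Dose Modification) discusses events associated with pembrolizumab that may be immunologic: "These adverse events may occur shortly after the first dose or several months after the last dose of treatment".

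On collection, Section 7.2 states: "All adverse events will be recorded from C1D1 through 30 days following cessation of treatment". Section 7.2.3.2, item 3, makes serious and non-serious ECIs reportable if "identified in this guidance document from the date of first dose through 30 days following cessation of treatment". In the Section 6.1 flow chart, the adverse event review row is marked at screening (serious events only), each cycle, discontinuation and the 30-day safety visit. It is blank for the 8-weekly follow-up visits and the 12-weekly survival contacts.

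For serious adverse events (SAEs), Section 5.8 says "serious adverse events will be collected for 90 days after the end of treatment as described in Section 7.2.3.1". Section 7.1.7.1 asks for follow-up and recording of "SAEs that occur within 90 days of the end of treatment or before initiation of a new anti-cancer treatment". Section 7.2.3.1, which Section 5.8 cites, covers SAEs of any cause "from the time the consent is signed through 30 days following cessation of treatment", or until new anti-cancer therapy if that comes sooner. It adds that an SAE judged related to Merck product must be reported whenever it comes to the investigator's notice.

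Two further statements bear on the cut-off. Section 5.5.1 says that "medications administered after 30 days after the last dose of trial treatment should be recorded for SAEs as defined in Section 7.2 and ECIs". Section 7.1.4.1 has adverse experiences graded and recorded into follow-up, with no end date.

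**The concern.** The ECI category is the plan's main instrument for immune toxicity, and its window closes at a point after which the plan itself expects such events to occur. Safety and tolerability are the phase I escalation objective (Section 3.1) and are listed among the trial's endpoints (Section 4.2.3).

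Non-serious does not mean unimportant here. Under Sections 5.2.1.2 and 5.6.1, Grade 2 pneumonitis leads to withholding of pembrolizumab and systemic corticosteroids. A second episode of Grade 2 or higher ends study therapy, and Section 7.1.7.3 allows some patients to be retreated after a treatment-free interval. A non-serious episode off treatment after day 30 could therefore be absent from the trial record that such a rule relies on.

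The conflicting SAE windows add a second problem. Staff following different sections would collect different data for the same event, and a safety table could not state one observation period.

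**Working it through.** The plan gives no rate or calculation to reproduce, so the check compares the stated windows.

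**Step 1. Windows after the last dose**

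| What | Section | Window |
|---|---|---|
| All adverse events | 7.2 | to day 30 |
| ECIs in the guidance document, serious or not | 7.2.3.2, item 3 | to day 30 |
| SAEs, any cause | 7.2.3.1 | to day 30, or new anti-cancer therapy if earlier |
| SAEs | 5.8 | to day 90, citing 7.2.3.1 |
| SAEs | 7.1.7.1 | within 90 days, or before new anti-cancer treatment |
| SAEs judged related to Merck product | 7.2.3.1 | no limit, but only if brought to the investigator's attention |
| Adverse experiences generally | 7.1.4.1 | into follow-up, no end stated |
| Concomitant medications for SAEs and ECIs | 5.5.1 | beyond day 30 |

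The two SAE windows differ by 90 − 30 = 60 days. Section 5.8 attributes its 90 days to a section that states 30.

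**Step 2. Follow two events with onset on day 45**

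- *A new, non-serious Grade 2 pneumonitis.* It falls outside Section 7.2 and outside Section 7.2.3.2, item 3. The SAE provisions do not apply. The rule in Section 7.1.7.1 that follows events above Grade 1 to resolution is tied to the safety visit and does not provide for a new onset after it. No flow-chart entry prompts anyone to ask. Only the general sentence in Section 7.1.4.1 could reach it, and no scheduled adverse event review supports that sentence.
- *A serious colitis.* Sections 5.8 and 7.1.7.1 collect it. The all-cause rule in Section 7.2.3.1 does not, but the related-event rule in the same section does if the investigator learns of it and judges it related. Section 7.2.3.2, item 3, excludes it as an ECI.

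The first event has no scheduled collection. The second is covered or not depending on the section followed.

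**Step 3. Could existing contacts close the gap?**

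Section 7.1.7.2 provides visits for some patients: "Subjects who discontinue trial treatment for a reason other than disease progression will move into the Follow-Up Phase". Imaging is every 56 ± 7 days, and the flow chart counts from discontinuation. The first visit is therefore due 56 − 7 = 49 to 56 + 7 = 63 days after discontinuation. If discontinuation coincides with the last dose, this lies within days 31–90. Section 5.2.1.2, however, allows up to 12 weeks (12 × 7 = 84 days) from the last dose for a toxicity to resolve before discontinuation. For a pembrolizumab-alone patient discontinued at that point, the earliest such visit would be 84 + 49 = 133 days after the last dose. Patients who have progressed have only telephone survival contacts every 12 weeks (Section 7.1.7.2.1). Existing contacts would reach many patients in time, but not all.

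**The case against.** The strongest reply is that the plan is inconsistent rather than silent. Section 7.1.4.1 extends recording into follow-up. Section 7.2.3.1 says non-serious ECIs are handled as SAEs are, which arguably carries over the longer or open-ended SAE rules. The ECI guidance document (Section 11.4) is not reproduced and may set a longer window. Section 5.5.1 may concern only ECIs that began before day 30 and are still being treated.

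Part of this stands. It would be wrong to say that no section could be read to capture these events, and Section 5.5.1 alone does not prove that new late ECIs were expected. But the handling sentence in Section 7.2.3.1 concerns how reports are forwarded, and its open-ended rule names only serious events. Section 7.2.3.2 sets an explicit 30-day limit for events identified in that same guidance document. No reading supplies a scheduled enquiry after the safety visit.

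A reader might also infer three stronger points that the documents do not support:

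- *That late immune toxicity as a whole goes unreported.* Serious events have 90-day cover in two sections, and related ones are reportable at any time once known.
- *That Arm B's toxicity is undercounted relative to Arm A.* This needs earlier stopping in Arm B. The documents do not show that, and longer disease control there could reverse the direction. A 90-day window would also still run from the last dose.
- *That a particular number of events will be lost.* No late-onset rate is given, and new anti-cancer therapy would end collection early for some patients.

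**Conclusion.** The point holds in limited form. As written, new non-serious immune-related events more than 30 days after the last dose have no scheduled collection, although the plan says such events can occur then. Serious events are partly covered, under windows that differ by 60 days and a cross-reference that does not match its target.

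The number of affected events cannot be derived from the documents. The dose-limiting toxicity assessment is unaffected, since Section 8.2.3 confines it to the first 21 days of treatment. What is weakened is the wider safety description of both arms. The conclusion assumes that the guidance document, which could not be checked, does not override the 30 days in Section 7.2.3.2. This is an inexpensive improvement to safety capture and does not threaten the primary efficacy comparison.

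**What to change.** Reconcile Sections 5.5.1, 5.8, 6.1, 7.1.4.1, 7.1.7.1, 7.2, 7.2.3.1 and 7.2.3.2 to one post-treatment collection window for SAEs, ECIs and immune-related adverse events, and check the guidance document against it. The 90 days already stated for SAEs, ending earlier if new anti-cancer therapy starts, would close the gap. Correct the citation in Section 5.8 accordingly.

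In the flow chart, mark an ECI and immune-related event query at the existing follow-up visits and survival calls that fall within the window. In the safety tables, show onset up to day 30 and onset on days 31–90 separately, by arm, so that the day-30 figures remain available.

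This changes data collection only. It needs a short amendment and no new visits or tests. It will produce a few more ECI reports, each with the 24-hour sponsor deadline and the two-working-day Merck deadline. Two limits remain: events visible only in laboratory results will be captured incompletely because no tests are added, and not every patient is guaranteed a contact within the window.

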## 7.2.4 Evaluating Adverse Events

An investigator who is a qualified physician will evaluate all adverse events according to the NCI Common Terminology Criteria for Adverse Events (CTCAE), version 4.0. Any adverse event which changes CTCAE grade over the course of a given episode will have each change of grade recorded on the adverse event case report forms/worksheets.

All adverse events regardless of CTCAE grade must also be evaluated for seriousness.

## **Table 10. Evaluating Adverse Events**

An investigator who is a qualified physician or APP, will evaluate all adverse events as to:

V4.0 CTCAE Grading	Grade 1	Mild; asymptomatic or mid symptoms; clinical or diagnostic observations only; intervention not indicated.									
•	Grade 2	Moderate; minimal, local or noninvasive intervention indicated; limiting age-appropriate instrumental ADL.									
	Grade 3	Severe or medically significant but not immediately life-threatening; hospitalization or prolongation or hospitalization indicated; disabling; limiting self-care ADL.									
	Grade 4	Grade 4 Life threatening consequences; urgent intervention indicated.									
	Grade 5	Death related to AE									
Seriousness	A serious adverse event is any adverse event occurring at any dose or during any use of Merck product that:										
	†Results in deat	th; or									
	†Is life threatening; or places the subject, in the view of the investigator, at immediate risk of death from the event as it occurred (Note: This does no										
	include an adverse event that, had it occurred in a more severe form, might have caused death.); or										
	†Results in a persistent or significant disability/incapacity (substantial disruption of one's ability to conduct normal life functions); or										
	†Results in or prolongs an existing inpatient hospitalization (hospitalization is defined as an inpatient admission, regardless of length of stay, even if the hospitalization is a precautionary measure for continued observation. (Note: Hospitalization [including hospitalization for an elective										
	procedure] for a preexisting condition which has not worsened does not constitute a serious adverse event.); or										
	†Is a congenital anomaly/birth defect (in offspring of subject taking the product regardless of time to diagnosis);or										
	Is a new cancer; (that is not a condition of the study) or										
	Is an overdose (whether accidental or intentional). Any adverse event associated with an overdose is considered a serious adverse event. An										
	overdose that is not associated with an adverse event is considered a non-serious event of clinical interest and must be reported within 24 hours.										
	Other important medical events that may not result in death, not be life threatening, or not require hospitalization may be considered a serious										
	adverse event when, based upon appropriate medical judgment, the event may jeopardize the subject and may require medical or surgical										
	intervention to prevent one of the outcomes listed previously (designated above by a †).										
Duration		and stop dates of the adverse event. If less than 1 day, indicate the appropriate length of time and units									
Action taken		event cause the Merck product to be discontinued?									
Relationship		oduct cause the adverse event? The determination of the likelihood that the Merck product caused the adverse event will be provided									
to test drug	causality noted o	r who is a qualified physician. The investigator's signed/dated initials on the source document or worksheet that supports the n the AE form, ensures that a medically qualified assessment of causality was done. This initialed document must be retained for the									
	required regulatory time frame. The criteria below are intended as reference guidelines to assist the investigator in assessing the likelihood of a										
		een the test drug and the adverse event based upon the available information.									
		omponents are to be used to assess the relationship between the Merck product and the AE; the greater the correlation with									
		and their respective elements (in number and/or intensity), the more likely the Merck product caused the adverse event (AE):									
	Exposure	Is there evidence that the subject was actually exposed to the Merck product such as: reliable history, acceptable compliance assessment (pill count, diary, etc.), expected pharmacologic effect, or measurement of drug/metabolite in bodily specimen?									
	Time Course	Did the AE follow in a reasonable temporal sequence from administration of the Merck product?									
		Is the time of onset of the AE compatible with a drug-induced effect (applies to trials with investigational medicinal product)?									
	Likely Cause  Is the AE not reasonably explained by another etiology such as underlying disease, other drug(s)/vaccine(s), or other host or environmental factors										

Relationship	The following of	components are to be used to assess the relationship between the test drug and the AE: (continued)					
to Merck	Dechallenge	Was the Merck product discontinued or dose/exposure/frequency reduced?					
product		If yes, did the AE resolve or improve?					
(continued)		If yes, this is a positive dechallenge. If no, this is a negative dechallenge.					
		(Note: This criterion is not applicable if: (1) the AE resulted in death or permanent disability; (2) the AE resolved/improved despite continuation of the Merck product; or (3) the trial is a single-dose drug trial); or (4) Merck product(s) is/are only used one time.)					
	Rechallenge	Was the subject re-exposed to the Merck product in this study?					
		If yes, did the AE recur or worsen?					
		If yes, this is a positive rechallenge. If no, this is a negative rechallenge.					
		(Note: This criterion is not applicable if: (1) the initial AE resulted in death or permanent disability, or (2) the trial is a single-dose drug trial); or (3) Merck product(s) is/are used only one time).					
		NOTE: IF A RECHALLENGE IS PLANNED FOR AN ADVERSE EVENT WHICH WAS SERIOUS AND WHICH MAY HAVE BEEN					
		CAUSED BY THE MERCK PRODUCT, OR IF REEXPOSURE TO THE MERCK PRODUCT POSES ADDITIONAL POTENTIAL					
		SIGNIFICANT RISK TO THE SUBJECT, THEN THE RECHALLENGE MUST BE APPROVED IN ADVANCE BY THE U.S.					
		CLINICAL MONITOR AS PER DOSE MODIFICATION GUIDELINES IN THE PROTOCOL.					
	Consistency	Is the clinical/pathological presentation of the AE consistent with previous knowledge regarding the Merck product or drug class					
	with Trial	pharmacology or toxicology?					
	Treatment						
	Profile						
		ill be reported on the case report forms /worksheets by an investigator who is a qualified physician according to his/her best clinical of the above elements.					
Record one of		Use the following scale of criteria as guidance (not all criteria must be present to be indicative of a Merck product relationship).					
Yes, there is a possibility of N relationship.		There is evidence of exposure to the Merck product. The temporal sequence of the AE onset relative to the administration of the Merck product is reasonable. The AE is more likely explained by the Merck product than by another cause.					
No, there is no possibility Mer relationship		Subject did not receive the Merck product OR temporal sequence of the AE onset relative to administration of the Merck product is not reasonable OR there is another obvious cause of the AE. (Also entered for a subject with overdose without an associated AE.)					

